## 7.9.9 Criteria for Early Termination of the Study

The trial may be terminated because of safety concerns. If termination is deemed appropriate, there will be timely communication with the FDA in accordance with the regulations (21 CFR 812.150 (devices)). The sponsor, Prollenium Medical Technologies, will initiate discussion as soon as possible about the appropriate course of action for the trial in question and for the investigational product. There will be immediate follow-up by the company to investigate any potential safety concern.

In the event of a vascular embolic event leading to skin necrosis, vision loss, or stroke, enrollment and treatment at the investigational site will be suspended and a root cause investigation will be conducted to determine the cause of the embolic event and whether the outcome was anticipated (the investigator did not properly follow the treatment SOP) or unanticipated (the investigator did properly follow the treatment SOP). If the latter situation is

observed, the entire study will be immediately suspended and no subjects will be enrolled until the event can be properly characterized and an appropriate treatment strategy to avoid this unanticipated event can be devised.

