#### 7.9.3.4 Adverse Events of Special Interest

Certain events will require more detailed and timely reporting. These include:

- any significant changes in vision. A one-line change in the Snellen chart is considered significant and requires reporting as an AESI.
- any events attributable to an embolic or ischemic cause (e.g., skin infarction)
- Any incidence of an event due to an embolic or ischemic cause or visual disturbances (including, but not limited to, any loss of vision, blurry vision, double vision, pain in or around eye, blind spot or shadow in the visual field, trouble moving eyes, etc.) MUST be immediately reported to the Medical Monitor by phone, email or fax. The investigator/coordinator must complete the AE source/CRF page and email or fax it to the Medical monitor as soon as possible after the investigator or coordinator has become aware of its occurrence. These reports will include the depth of injection, the injection volume, the symptoms that were observed, the time to onset, time to resolution, and any

interventions that were implemented. The Sponsor will notify the FDA within 10 working days regardless of relation to investigational device.

In the event of blindness or any ophthalmic signs or symptoms, subjects will undergo immediate evaluation by a retina specialist.

Refer to Appendix 1: Filler First Aid Protocol.

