#### WARNINGS

- Defer use of *PN40082* at specific sites in which an active inflammatory process (skin eruptions such as cysts, pimples, rashes, or hives) or infection is present until the process has been controlled.
- Injection site reactions (e.g., lip swelling, lip pain, and contusion) to *PN40082*, including short-term minor or moderate inflammatory symptoms starting shortly after treatment of lips
- PN40082 must not be implanted into blood vessels. Localized superficial necrosis and scarring may occur after injection in or near vessels, such as in the lips, nose, or glabellar area. It is thought to result from the injury, obstruction, or compromise of blood vessels.
- Delayed onset inflammatory papules have been reported following the use of dermal fillers. Inflammatory papules that may occur rarely should be considered and treated as a soft tissue infection.

- Injections of 4.0 mL or greater (upper and lower lip combined) per treatment session increases the occurrence of injection site reactions. If a volume of more than 3 mL is needed to achieve optimal correction, a follow-up treatment session is recommended.
- As with all dermal filler procedures, PN40082 should not be used in vascular rich areas.
   Use of similar products in these areas, such as glabella and nose, has resulted in cases of vascular embolization and symptoms consistent with ocular vessel occlusion, such as blindness.

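### The only mandatory site hold, in Section 7.9.9, is worded for embolic events and so, read literally, leaves out skin necrosis from a non-embolic ischemic cause

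*Combined protocol and SAP*

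**What the plan says.** Section 7.9.9 has two parts. The first paragraph is general: the trial may be terminated for safety reasons, the sponsor opens a discussion as soon as it can, and "There will be immediate follow-up by the company to investigate any potential safety concern". Termination is discretionary, and nothing in that paragraph suspends enrollment or treatment.

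The second paragraph is the mandatory rule. It opens "In the event of a vascular embolic event leading to skin necrosis, vision loss, or stroke, enrollment and treatment at the investigational site", which is then to be suspended. A root cause investigation is to be "conducted to determine the cause of the embolic event and whether the outcome was anticipated", where anticipated means that the investigator did not keep to the treatment SOP. If the SOP was followed, "the entire study will be immediately suspended and no subjects will be enrolled until the event can be properly characterized" and a way of avoiding a repeat has been worked out.

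Section 7.9.3.4 defines adverse events of special interest more widely, to include "any events attributable to an embolic or ischemic cause (e.g., skin infarction"). Sections 7.1 and 7.9.2 use the same pairing of embolic and ischemic. These events go to the Medical Monitor immediately and to the FDA within 10 working days. For ophthalmic signs, "subjects will undergo immediate evaluation by a retina specialist".

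The Warnings in both Instructions for Use (Appendices 2 and 3) list localized superficial necrosis as possible when filler is injected into a vessel or close to one, and they name the lips. On mechanism they say: "It is thought to result from the injury, obstruction, or compromise of blood vessels".

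**The concern.** The rule that stops treatment at a site depends on the mechanism of the event as well as on its outcome. Skin necrosis is the first outcome that 7.9.9 lists, so the sponsor already regards it as serious enough for a hold. Yet a necrosis put down to injury or compromise of a vessel, rather than to embolized filler, does not meet the trigger as worded. The investigation is also worded for an embolic event, and the study-wide step follows from that investigation, so all three mandatory steps turn on one adjective.

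At stake is whether a site may go on treating new subjects, in an elective cosmetic procedure, after a non-embolic ischemic necrosis and before anyone has examined why it happened. As written it may, unless the sponsor intervenes. The point concerns necrosis; the mismatch has little bearing on vision loss or stroke.

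**Working it through.** The plan states no figure on this point, so the check is mainly textual: does any other provision require a site to stop?

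| Provision | Events covered | Required action | Must the site stop? |
|---|---|---|---|
| 7.9.9, second paragraph | Embolic, with necrosis, vision loss or stroke | Site suspended, cause investigated | Yes |
| 7.9.9, study-wide step | Same trigger, with the SOP followed | Whole study suspended | Yes, but only through the same trigger |
| 7.9.9, first paragraph | Any safety concern | Sponsor follow-up; termination possible | No |
| 7.9.3.4 | Embolic or ischemic; vision changes | Immediate report; FDA notice; retina specialist for eye signs | No |
| 7.9.7 | SAEs | Form within 24 hours, written follow-up within 5 calendar days, IRB report if serious and unexpected | No |
| 7.4.3 | Persistent blanching | Contact the Medical Monitor | No |
| 7.3.3 | A subject at risk | Withdraw that subject | No |
| Appendix 1 | Recognised intravascular event | Stop injecting; first aid | No; in context this concerns that subject's session |

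**Coverage.** Take a necrosis judged to be ischemic but not embolic. It falls under 7.9.3.4 and, if serious, under 7.9.7. It does not fall under the second paragraph of 7.9.9. No other row stops the site.

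**Suspicion.** Section 7.9.9 does not say that a suspected cause is enough. It does place the suspension before the investigation, and Appendix 1 tells staff to act on signs. This part is a matter of clarity.

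**Exposure.** Inputs:
- Sites: 5 (Synopsis).
- Treatment period: 20 months of study less about 6 months of participation per subject = 14 months (Synopsis).
- Subjects: 158 as the upper limit (the Synopsis expects fewer); 80 is an assumed lower value.

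Subjects per site per month = N / (months × sites).
- N = 80: 80 / (14 × 5) = 1.14
- N = 158: 158 / (14 × 5) = 2.26

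Even accrual is doubtful, because roll-overs from PRO 2018-03 are to be treated within 14 days of their Day 168 call. If treatment is bunched into 7 months (assumed):
- N = 80: 80 / (7 × 5) = 2.29
- N = 158: 158 / (7 × 5) = 4.51

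The same figures serve twice: as the further subjects treated per month at a site that is not held, and as the treatments deferred per month at a site that is. A monthly rate is the natural unit, because no text sets a time by which the sponsor must decide. The 24-hour and 5-day limits in 7.9.7 govern paperwork.

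**The case against.** Three arguments count against the point.

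First, Appendix 1 steers sites toward an intravascular explanation. Its instructions for skin infarction follow a call to recognise intravascular events and refer to a vessel entered by accident. A site that saw an infarction would probably treat it as embolic and hold. The gap opens only once someone has classed the event as ischemic but not embolic, and no step asks for that classification before the hold. This stands, and it makes the gap narrow. It does not close the gap, because the trigger still names the cause.

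Second, a reporting definition may properly be wider than a stopping rule, and localized superficial necrosis is a labelled risk. The mismatch with 7.9.3.4 is therefore not an error in itself. This stands in part. For the site hold, 7.9.9 already lists necrosis as an outcome that warrants suspension and gives no reason to separate cases by mechanism. For the study-wide step the argument stands in full.

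Third, the sponsor learns of such an event at once, must follow it up, and must notify the FDA. This also stands. These duties inform and investigate; they do not suspend treatment.

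A reader might infer that a site has to prove embolism before it stops. The documents do not support that, since suspension precedes the investigation. Nor do they support the inference that a non-embolic necrosis would go unmonitored.

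**Conclusion.** The point holds as a minor, cheap improvement. Read literally, the only mandatory site hold omits skin necrosis from a non-embolic ischemic cause, and no other provision requires the site to stop. That the trigger is silent on suspected causes is a secondary matter of clarity.

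In numbers the gap is small: about 1.1 to 2.3 further subjects per month at the affected site under even accrual, or 2.3 to 4.5 if accrual is bunched. These figures rest on an assumed lower sample size and assumed accrual patterns. They measure exposure to treatment. A reader might take them as expected harm, but the documents give no rate for such events. The case rests on the seriousness of an outcome that the rule already lists.

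A reader might also infer that non-embolic necrosis should suspend the whole study. The documents do not support that. The study-wide suspension lasts until a way of avoiding the event is found, and for a labelled risk that arose with the SOP followed there may be none. No endpoint, sample size or analysis is affected.

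**What to change.** Make three small edits to the second paragraph of 7.9.9:

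1. In the trigger, insert *known or suspected* before *vascular*, and *or ischemic* after *embolic*. The three outcomes and the suspension stay as they are.
2. Where the purpose of the root cause investigation is stated, drop the word *embolic*, so that the inquiry matches the wider trigger.
3. Limit the study-wide sentence expressly to embolic events. Without this, the second edit would carry the automatic suspension over to non-embolic events. Study-wide action after a non-embolic ischemic event stays with the sponsor under the first paragraph of 7.9.9.

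Two additions may suggest themselves and should be left out. A condition that the event be related to the injection would narrow the present rule, which has none. So would an exemption for small acuity changes. Section 7.9.3.4 says "A one-line change in the Snellen chart is considered significant and requires reporting as an AESI", but that is a reporting rule and needs no counterpart here.

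The cost is a protocol revision with sponsor and IRB approval (Sections 9.2 and 10.5) and an occasional hold at one site. Such a hold defers about 1 to 2 treatments per month under even accrual, or about 2 to 5 if accrual is bunched. Without a relatedness condition, an unrelated ischemic stroke during the 168-day follow-up could also hold a site. The present wording already does this for an unrelated embolic stroke.

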## 7.9.10 Withdrawal and Unblinding of Treatment Due to Safety Observations

#### **7.9.10.1 Withdrawal**

See section 7.3.3 for the criteria for withdrawing a subject. If a subject is withdrawn from the study, the activities specified for Visit 2/Month 1 on the schedule of study activities (Section 2) should be completed if possible.

## 7.9.10.2 Unblinding Treatment for a Subject During the Study

Unblinding by the investigator should occur only in the event of an AE or SAE for which it is necessary to know the study treatment to determine an appropriate course of therapy for the subject. In the event of an emergency that requires breaking of the study blind, the Investigator can unblind the subject without prior contact with the Medical Monitor although the Investigator will immediately notify the Medical Monitor accompanied by a written explanation of the reason why the blind was broken. In the event of an emergency that requires breaking of the study blind, the randomization code will be maintained by each unblinded Treating Investigator that can be opened to reveal the study device to the applicable staff. In the event the unblinded Treating Investigator is not available, the site should designate another unblinded staff member not involved in the study conduct to access the randomization code for that subject. Note this can be done WITHOUT informing the blinded Evaluating Investigator and thus maintaining the study blind. If unblinding occurs, the subject must be withdrawn from the study.

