#### 1 SYNOPSIS

**Title of Study:** A Multicenter, Double-blind, Randomized, Controlled, Roll-over Study of the Safety and Pain Associated with Injections of PN40082, RV001 with Topical Anesthetic or RV001 for Lip Augmentation

Name of Sponsor: Prollenium Medical Technologies Inc.

Name of Finished Product: PN40082®

**Device Composition:** PN40082 - Hyaluronic acid gel with lidocaine (0.3% w/w) RV001- Hyaluronic acid gel without lidocaine

**Objectives:** To evaluate the safety of repeat injections and pain associated with injection of PN40082 and comparative pain associated with RV001 with a topical anesthetic and RV001 for lip augmentation.

**Study Design:** This is a multicenter, double-blind, randomized, controlled, roll-over clinical study of treatment of subjects seeking lip augmentation who received treatment with either PN40082 or Restylane Silk in prior Protocol PRO 2018-02, and PN40082 in prior Protocol PRO 2018-03. Subjects meeting the inclusion/exclusion criteria will receive a single additional treatment with either RV001, RV001 with a topical anesthetic, or PN40082. The Evaluating Investigator will be blinded to the treatment. Injections of the study device will be performed by an unblinded Treating Investigator.

At each visit the blinded Evaluating Investigator evaluations and subject evaluations of the treated areas will be performed and recorded. Visits and telephone contacts will occur at:

Visit 1 / Day 1 — baseline and treatment

- Day 3 (±2 days) Safety follow-up telephone call
- Day 14 (±2 days) Safety follow-up telephone call

Visit 2 / Day 28 ( $\pm 2$  days) / Month 1 – End of Study Visit

- Day 56 (±4 days) / Month 2 Safety follow-up telephone call
- Day 168 (±7 days) / Month 6 End of Study telephone call

Efficacy evaluations are:

Subject pain score (VAS) at time of injection

Subject pain score (VAS) at 15 minutes after injection

Lip Fullness Grading Scale (LFGS) - overall lip fullness considering both lips together, fullness of the upper lip, and fullness of the lower lip

Perioral lines at rest severity scale (POL) - overall perioral lines at rest severity considering both lips together, perioral lines at rest severity of the upper lip, and perioral lines at rest severity of the lower lip

Patient Global Aesthetic Improvement (pGAI)

Investigator Global Aesthetic Improvement (iGAI)

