## 7.2 Beginning and End of Study

A subject is considered to be enrolled in the study when he/she has provided written informed consent.

A subject is considered to have completed the study after he/she has completed the Day 168 Month 6/End of study telephone call.

A subject is considered to have withdrawn after he/she has withdrawn consent or has been withdrawn under the conditions specified in Section 7.3.3.

A subject is considered to have been lost to follow-up if he/she cannot be contacted by the investigator. The investigator will document efforts to attempt to reach the subject at least twice by telephone and will send a certified letter before considering the subject lost to follow-up. The end of participation for a subject lost to follow-up is documented as the date of the certified letter.

Each subject will be monitored for the occurrence of AEs, including serious adverse events (SAEs), starting immediately after treatment initiation. Each subject will be followed for safety monitoring until he/she is discharged from the study.

Follow-up procedures related to pregnancy, AEs, or SAEs may continue beyond the end of the study.

Each subject will participate in the study for approximately 6 months from the time he/she signs the ICF through the final contact. After determination of eligibility at Visit 1/Day 1, each subject will be treated with study device.

It is anticipated that the duration of this study will be 20 months from the beginning to the end of the study (first subject signing the ICF to last contact with last subject).

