# 7.3.3 Subject Withdrawal Criteria

A subject may withdraw from the study at any time for any reason.

A subject will be withdrawn from the study if his/her safety or well-being is determined to be at risk. Withdrawal will be made at the discretion of the investigator or at the subject's request.

A subject must withdraw from the study for any of the following reasons:

- The subject or legal representative withdraws consent
- There is a significant protocol violation as determined by the Sponsor or medical monitor.

A subject may be withdrawn from the study for any of the following reasons:

- Lost to follow-up
- Investigator discretion

Withdrawal is permanent; after a subject has been withdrawn, he/she will not be allowed to enroll again.

If a subject is withdrawn from the study for any reason, the EOS or Early Termination procedures (Visit 2/Month 1) should be completed and any outstanding data and study device should be collected. Data, including the date and primary reason for withdrawal, must be documented on the EOS case report form (CRF) and source document.

If a subject withdraws from the study at any time due to an AE, the reason for withdrawal, the nature of the AE, and its clinical course must be fully documented. The investigator must strive to follow the subject until the AE has resolved, become clinically insignificant, is stabilized, or the subject is lost to follow-up. For any SAE, follow procedures provided in Section 7.9.7.

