### 7.5 Study Schedule

The visit-by-visit schedule of study activities is provided in Section 2. The timing of each visit is relative to Day 1, which is defined as the day the subject is treated in PRO 2019-02.

All visits should be performed within the windows specified on the schedule of study activities. Every attempt should be made to have each subject attend each visit as scheduled. If a subject is unable to attend a visit within the specified window the visit should be scheduled as closely as possible to the applicable window.

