#### 7.9.5 Monitoring Adverse Events

Each subject will be monitored for the occurrence of AEs, including SAEs, immediately after treatment initiation. Each subject will be followed for safety monitoring until discharged from the study. Follow-up procedures related to pregnancy or AEs or SAEs may continue beyond the end of the study.

Subjects will be questioned and/or examined by the investigator or a qualified designee for occurrence of AEs throughout the study. The presence or absence of specific AEs should not be elicited from subjects. In addition, subjects will be instructed to record AEs on the subject diary card during the 2 weeks after treatment, and on the subject diary card dispensed at Visit 2 for the remainder of the study. Subjects having AEs will be monitored with relevant clinical assessments and laboratory tests, as determined by the investigator.

AEs, actions taken as a result of AEs, and follow-up results must be recorded on the CRF, as well as in the subject's source documentation.

For all AEs that require the subject to be withdrawn from the study and SAEs, relevant clinical assessments will be repeated as clinically appropriate until final resolution or stabilization of the event(s).

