## 7.9.7 Reporting Safety Observations

Any SAE, whether deemed device-related or not, must be reported to the Sponsor or designee by telephone, email, or fax as soon as possible after the investigator or coordinator has become aware of its occurrence. The investigator/coordinator must complete a Serious Adverse Event (SAE) Form and email or fax it to the Sponsor or designee along with the subject's Adverse Events Log and Concomitant Medications Log within 24 hours of notification of the event. The Sponsor will notify the FDA of device-related SAEs.

Designee and Sponsor contact details:

The investigator must be prepared to supply the medical monitor with the following information:

- 1. Investigator name and site number
- Protocol number
- 3. Subject ID (screening/randomization) number
- 4. Subject initials and date of birth

- Subject demographics
- 6. Clinical event
  - a. description
  - b. date of onset
  - c. severity
  - d. treatment (including hospitalization)
  - e. relationship to study device
  - f. action taken regarding study device
  - g. if the AE was fatal or life-threatening:
    - i. cause of death (whether or not the death was related to study device)
    - ii. autopsy findings (if available)

The Sponsor must submit a written summary of the clinical course of any life-threatening SAE and related subject information to the FDA within 7 days. Serious and unexpected AEs that are not life-threatening must be reported to the FDA within 15 calendar days. Any serious and unexpected AE (including all deaths) must also be reported to the Institutional Review Board (IRB) by the investigator according to IRB reporting requirements and documentation of this report sent to the Sponsor or designee.

The investigator must provide a follow-up written report within 5 calendar days of reporting the event to the medical monitor. The written report must contain a full description of the event and any sequelae. Subjects who have had an SAE must be followed clinically until all parameters (including laboratory) have either returned to normal or are stabilized.

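### Unblinding for an adverse event forces withdrawal from the study, although treatment ended on Day 1 and nothing keeps the remaining safety calls

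*Combined protocol and SAP*

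**What the plan says.** Section 7.9.10.2 permits the investigator to break the blind only where an AE or SAE makes knowledge of the treatment necessary for choosing therapy. It then states: "If unblinding occurs, the subject must be withdrawn from the study". The same section says of the code break: "Note this can be done WITHOUT informing the blinded Evaluating Investigator and thus maintaining the study blind".

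Treatment is a single session. Under the Synopsis, subjects "will receive a single additional treatment with either RV001, RV001 with a topical anesthetic, or PN40082". Section 7.5 adds: "The timing of each visit is relative to Day 1, which is defined as the day the subject is treated in PRO 2019-02". Scheduled contacts after that are calls on Days 3 and 14, Visit 2 on Day 28, and calls on Days 56 and 168. Each call assesses AEs and asks directly about vision and stroke symptoms (Sections 7.7.2, 7.7.4, 7.7.5).

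A withdrawn subject keeps some follow-up:

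- Sections 7.3.3 and 7.9.10.1 ask for the Visit 2 procedures, the latter only if possible.
- For a withdrawal due to an AE, Section 7.3.3 says: "The investigator must strive to follow the subject until the AE has resolved, become clinically insignificant, is stabilized".
- For SAEs, Section 7.9.7 says: "Subjects who have had an SAE must be followed clinically until all parameters (including laboratory) have either returned to normal or are stabilized".
- Section 7.9.5 allows more: "Follow-up procedures related to pregnancy or AEs or SAEs may continue beyond the end of the study".

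On who counts as withdrawn, Section 7.2 says: "A subject is considered to have withdrawn after he/she has withdrawn consent or has been withdrawn under the conditions specified in Section 7.3.3". Section 7.3.3 does not name unblinding.

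**The concern.** Withdrawal from the study is a different thing from stopping treatment. Here no treatment is left to stop, so the rule's only practical effect is on data collection. It does little for the blind either: the section itself says the code can be broken without telling the evaluator, and after Visit 2 no blinded rating or pain score is scheduled.

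The subjects affected are not a random subset. Each has, by definition, had an event serious or puzzling enough to need the code. They remain in the all-treated summaries (Sections 8.1 and 8.3) while planned questioning about further events stops. Later new preferred terms, or a rise to a higher severity or relationship category, could go uncounted. Safety of repeat injections is a stated objective (Section 6), and the Synopsis plans to compare AE incidence across three studies, so gaps in late surveillance matter even when few.

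**Working it through.** The plan states no figure on this point, so there is none to reproduce. The check has a reading of the text and some arithmetic.

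**Reading.** Sections 7.2, 7.3.3, 7.9.4, 7.9.5, 7.9.7, 7.9.10.1 and 7.9.10.2 were compared.

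- Sections 7.3.3, 7.9.5 and 7.9.7 follow a known event until it resolves or stabilizes.
- Sections 7.3.3 and 7.9.10.1 ask for one set of Visit 2 procedures.
- Sections 7.2 and 7.9.5 run general safety monitoring until discharge from the study.
- None says that a withdrawn or unblinded subject keeps the remaining calls.
- Sections 7.2 and 7.9.10.1 refer to Section 7.3.3 for the withdrawal criteria. Section 7.3.3 omits unblinding, although its clauses on subject safety and investigator discretion may cover some cases.

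**Scheduled follow-up lost.** Calls fall on Days 3, 14, 56 and 168 (Section 7.1). With withdrawal on nominal day d, the days lost are 168 − d, and the share is taken of the 167 days from Day 1 to Day 168.

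| Withdrawal | Calls left | Days to Day 168 | Share of 167 |
|---|---|---|---|
| Day 1 | 4 | 168 − 1 = 167 | 100% |
| After Day 3 call | 3 | 168 − 3 = 165 | 98.8% |
| After Day 14 call | 2 | 168 − 14 = 154 | 92.2% |
| Day 28 | 2 | 168 − 28 = 140 | 83.8% |
| After Day 56 call | 1 | 168 − 56 = 112 | 67.1% |

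These are upper bounds, because follow-up of the triggering event may bring contact. For the first three rows, Visit 2 procedures done at the usual Day 28 would also leave only the last 140 days and two calls uncovered; the text does not say whether they are done then or at withdrawal.

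**Effect on a table row.** Fewer than 158 subjects are anticipated (Synopsis), so at most 157. At 1:1:1 (Section 7.4.2), 157/3 = 52.3, or about 52 per arm. One missed event is 1/52 = 1.9 percentage points. This is the smallest per-event effect, since smaller arms give larger percentages: with an assumed 20 per arm it is 1/20 = 5.0 points. If no later event occurs, the effect is 0.

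**Chance of seeing a late event.** Assume k unblinded subjects contribute no late observation and each subject has late-event risk p. The documents give neither figure. The loss in the probability of seeing at least one such event among n subjects is (1 − p)^(n − k) − (1 − p)^n.

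- All arms, n = 157, k = 1 to 3, p = 1% to 5%: 0.0 to 0.6 points. The largest is 0.99^154 − 0.99^157 = 0.006.
- One arm, n = 52, all k in that arm: 0.4 to 2.2 points. The largest is 0.98^49 − 0.98^52 = 0.022.
- One arm, assumed n = 20, k = 3: 2.5 to 6.0 points.

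No diary loss is counted. Section 7.9.5 mentions a diary dispensed at Visit 2, whereas Sections 2, 7.6.25 and 7.7.3 describe only one, given at Visit 1 and collected at Visit 2. That conflict needs reconciling separately.

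**The case against.** The strongest reply is that the trigger will be very rare. All arms inject a hyaluronic acid gel at 25 mg/mL and differ in lidocaine. Known hypersensitivity to amide anesthetics or injectable hyaluronic acid is excluded. The first-aid steps in Appendix 1 for skin infarction, visual symptoms and stroke do not depend on the arm, and the Treating Investigator already knows the assignment. A code break for the events that the calls target may never be needed. This stands, and it is why the effect is rated small.

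Second, the protocol never equates withdrawal with discharge, so a site might continue the calls. That is possible. But Section 7.3.3 makes withdrawal permanent and asks only for Visit 2 procedures and event follow-up; a site following the text has no instruction to keep calling.

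Third, the same calls are not expressly kept after other withdrawals, such as for pregnancy (Section 7.9.4) or a protocol violation, so the remedy is narrow. That is true. Unblinding is nonetheless a clear case in which a mandatory rule removes an already treated subject who may be willing to continue.

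Fourth, flagging ratings made after a code break could conflict with Section 8.1, which summarizes all treated subjects. The flag only makes an exclusion possible. The two Day 1 pain scores will usually precede any code break.

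**Conclusion.** The concern holds as a cheap improvement with a small expected effect. The rule is explicit, treatment is complete on Day 1, and no section preserves the remaining calls. What is lost is scheduled surveillance for new or worsening events; the triggering event is still followed, and the proportion with any TEAE is unchanged if that event is already counted.

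Per affected subject the loss is at most 4 calls and 167 days. At study level, with an assumed 1 to 3 unblinded subjects, the loss in detection probability is at most 0.6 points overall and 2.2 points in one arm at the enrolment ceiling; it grows if enrolment is lower. Safety summaries are descriptive. Section 8 leaves the handling of missing data to an SAP whose text is not in the documents, but no analysis rule can recover events that were never asked about.

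**What to change.** Replace the last sentence of Section 7.9.10.2 with wording to this effect: a subject whose assignment is unblinded and who still consents remains in follow-up for Visit 2 and every remaining scheduled safety call through Day 168. In addition:

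- Record the date of unblinding and who learned the assignment.
- Flag ratings made by any person after that person's blind was broken, so that they can be left out of the blinded efficacy summaries. The SAP should say how the flag is used, given the all-treated population of Section 8.1.
- Reconcile Sections 7.2, 7.3.3, 7.9.10.1 and 7.9.10.2 so that they agree on the status of an unblinded subject.
- Leave the other withdrawal criteria and the conditions for breaking the code unchanged.

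The cost is a short amendment with Sponsor and IRB approval before implementation (Sections 9.2 and 10.5) at five sites, plus one date, one flag and a record of who was unblinded on the CRF. The calls are already in the schedule.
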